2.2. Outcome Measures

2.2.1. Primary outcome:

Absolute BMD (g/cm²) at 2 years from the date of randomisation, assessed by a standard DEXA scan of the lumbar spine.

2.2.2. Secondary outcomes:

The secondary outcomes will be measured at different stages throughout the trial.

- Absolute BMD (g/cm²) in lumbar spine at 1 and 2 years.
- Absolute BMD (g/cm²) in hip at 1 and 2 years.
- T-score category (≤ -2.5 , > -2.5 to ≤ -1 , > -1) for BMD at lumbar spine at 1 and 2 years.
- T-score category for BMD at hip at 1 and 2 years.

Trial name:	Premature Ovarian Insufficiency Study of Effectiveness of hormonal therapy	Protocol version:	4.0	date:	01 Oct 2024	Page:	20
-------------	--	-------------------	-----	-------	-------------	-------	----

- Individual domains (vasomotor, psychosocial, physical and sexual) and summary score of Menopause Specific Quality of Life (MENQOL-I)-Intervention questionnaire at 3, 6 and 12 months then annually.
- Sexual function (pleasure, discomfort and frequency) measured by the Sexual Activity Questionnaire (SAQ)² at 3, 6, 12 months then annually.
- Work Productivity (absenteeism, presenteeism, work productivity loss and activity impairment), using the Work Productivity and Activity Impairment (WPAI) Scale (Specific health Problem)³ at 3, 6, 12 months then annually.
- Weight (kg) at 3, 6, and 12 months then annually.
- Systolic blood pressure (mm Hg) at 3, 6 and 12 months then annually.
- Diastolic blood pressure (mm Hg) at 3, 6 and 12 months then annually.
- Pregnancy and pregnancy outcome.
- Satisfaction with treatment, on a 5-point Likert scale at 3, 6 and 12 months then annually.
- Change or cessation of treatment at 3, 6 and 12 months then annually.
- Adverse events at 3, 6 and 12 months and then annually. Specific minor-side effects collected will include breast pain, nausea, headaches, skin or hair changes and unscheduled bleeding (see Section 9.2) as well as more serious events such as venous thromboembolism. All serious adverse events will be collected and causal relationship with treatment considered.
- Diagnosis of cancer, cardiovascular disease, cognitive impairment, bone fractures and mortality will be collected from routine data sources up to 5 years.

Sub-study

- Bone metabolism markers, liver function tests, bone profile, and 1,25 Vitamin D. Blood and urine samples will be collected in a subset of participants from selected sites, at baseline, 3 and 12 months (not reported until the end of the study).

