8.2. Schedule of Assessments

8.2.1. Enrolment and baseline

a) Identify potentially eligible patient

All potentially eligible patients should be approached and provided with information about the trial. This information will be entered onto the patient screening/enrolment log at each recruiting site. Patients that decline participation are not obliged to give a reason, however this will be recorded where this is known. Sites will be required to provide a summary of screening data on an ongoing basis during the recruitment period which will be reviewed regularly by the Trial Management Group (TMG) and oversight committees.

b) Informed Consent

Informed consent will be obtained as described in section 5. If a patient requires a washout period then eligibility will need to be re-confirmed prior to collecting baseline data.

c) Washout

Eligible women who are already on COC/HRT/testosterone treatment are required to stop treatment for a washout period of a minimum of 4 weeks. This is to ensure a return to pre-treatment hormone levels before performing baseline assessments.

d) Confirm Eligibility

Eligibility will be confirmed by the principal investigator or delegated trial doctor using the eligibility checklist form once informed consent and baseline data have been obtained.

e) Baseline data collection

After informed consent (and washout if applicable), baseline visit data will be collected by a member of the site research team and will include:

1. Patient demographics
2. Lifestyle factors e.g. smoking, alcohol, exercise habits
3. Use of medication e.g. prescribed, complementary and supplements
4. Pregnancy and breastfeeding
5. BMD (DEXA bone density measurement of lumbar spine and hip)
6. Quality of life (MENQOL-I questionnaire)
7. Sexual function (SAQ)
8. Work productivity (WPAI questionnaire)
9. Blood pressure (BP) and weight (refer to details below for BP measurement)
10. Height (measured at visit)
11. Blood and/or urine samples for bone and CVD biomarkers (selected sites only)

Trial name:	Premature Ovarian Insufficiency Study of Effectiveness of hormonal therapy	Protocol version:	4.0	date:	01 Oct 2024	Page:	31
-------------	--	-------------------	-----	-------	-------------	-------	----

12. Karyotype analysis (selected sites only and if clinically appropriate and not done prior to entering trial.

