13.3. Analysis of Outcome Measures

The analysis and reporting of the trial will be in accordance with CONSORT guidelines. A full statistical analysis plan (SAP) will be developed and agreed prior to database lock for the analysis of the primary outcome at 2 years.

Trial name:	Premature Ovarian Insufficiency Study of Effectiveness of hormonal therapy	Protocol version:	4.0	date:	01 Oct 2024	Page:	43
-------------	--	-------------------	-----	-------	-------------	-------	----

Appropriate descriptive statistics (mean, standard deviation, median, lower and upper quartiles, minimum, maximum or frequencies and percentages) for the demographic and clinical outcome measures at baseline will be used to assess balance between the randomised arms at baseline, but no formal statistical comparisons will be performed. Baseline characteristics will also be descriptively compared between those randomised and those analysed to see if the attrition has introduced any imbalances. Descriptive statistics appropriate for the outcome will also be presented for all outcomes at all collected time points by treatment group.

The primary comparative analysis will be based on intention-to-treat, analysing participants in the groups to which they were randomised. The evaluation of the primary outcome of BMD in the lumbar spine at 2 years will be performed using a mixed effects model to allow for all available follow-up data (1 year, 2 year) to be used, adjusted for the baseline BMD in the lumbar spine and the minimisation variables as fixed effects except site which will be entered as a random effect. The model will include a treatment by time interaction to obtain the estimates of treatment effect at each follow-up time, with 2 years being the primary evaluation. An interaction between each covariate and time will be added to get a different adjustment for each covariate at each time point. The estimated between group effect will be presented using the difference in means, with a 95% confidence interval. The primary treatment comparison will be the contrast between allocated treatment groups at 2 years.

Sensitivity analyses for the primary outcome will include:

- Complete case analysis based on observed outcome data at 2 years
- Use of multiple imputation with auxiliary variables (if applicable) not included in the primary analysis also included in the imputation model.

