- Adjustment for any other baseline variable (if applicable) with marked imbalance between the two treatment groups

Supplementary analyses for the primary outcome will investigate potential effects of compliance with allocated treatment using complier average causal effect (CACE) analysis (or per-protocol analysis should there be high crossover rates making CACE identification impossible) and estimate an overall time-averaged between-group effect over the 2 years to compare the overall rate of change in BMD between groups.

Main analyses of secondary outcomes will be based on intention-to-treat, analysing participants in the groups to which they were randomised, regardless of adherence with allocation. Sensitivity analyses (as described for the primary outcome) may also be performed for key secondary outcomes such as blood pressure, MENQOL-I, and BMD at 1 year and 2 years. Ordered logistic regression models will be used to compare the total lumbar spine and hip T-score categories (≤ -2.5 , > -2.5 to ≤ -1 , > -1) between groups, adjusted for the minimisation variables; however, should there be only a small number of participants in one of the categories then categories will be collapsed into two for analysis and logistic regression used. Between-group comparison of secondary outcomes will be based on an appropriate regression for the outcome adjusted for the minimisation variables and baseline outcome measure for continuous variables if available. For repeated measures, appropriate mixed-effect models for the outcome (linear for continuous outcomes and logistic for binary), adjusted for the minimisation variables, will be used to estimate the difference between groups at each time point. Supplementary analysis of key secondary outcomes may also be conducted according to actual treatment used if the percentage of women who stop using their allocated treatment or switch to the other treatment is high.

Adverse events will be presented descriptively only and will be summarised according to both the allocated group and the treatment received.

Trial name:	Premature Ovarian Insufficiency Study of Effectiveness of hormonal therapy	Protocol version:	4.0	date:	01 Oct 2024	Page:	44
-------------	--	-------------------	-----	-------	-------------	-------	----

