Mixed-effect models, with similar adjustments as described for analysis of the primary outcome, will be used to compare BMD and key secondary outcomes between each route of HRT administration (oral and transdermal) HRT and COC and between oral HRT and transdermal HRT (non-randomised comparison). Key secondary outcomes to be compared will be specified in the SAP.

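### Two adjacent rules in Protocol 13.3 give different covariates for continuous secondary outcomes; the repeated-measures rule leaves out the baseline value

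*Protocol*

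**What the plan says.** Protocol section 13.3 sets covariates in four places.

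- **Primary outcome.** The mixed model for lumbar spine BMD is "adjusted for the baseline BMD in the lumbar spine and the minimisation variables as fixed effects", with site as a random effect and a time interaction for each covariate. It yields a treatment contrast at 1 year and at 2 years.
- **Secondary outcomes, general rule.** The regression is "adjusted for the minimisation variables and baseline outcome measure for continuous variables if available".
- **Secondary outcomes, repeated measures (the next sentence).** "For repeated measures, appropriate mixed-effect models for the outcome (linear for continuous outcomes and logistic for binary), adjusted for the minimisation variables".
- **HRT route comparisons.** BMD and key secondary outcomes are compared by mixed models "with similar adjustments as described for analysis of the primary outcome", which brings baseline in.

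Section 2.2.2 lists the continuous secondary outcomes. All have several follow-up times, for example "Systolic blood pressure (mm Hg) at 3, 6 and 12 months then annually". It also lists "Absolute BMD (g/cm²) in lumbar spine at 1 and 2 years" as a secondary outcome, and section 13.3 speaks of "key secondary outcomes such as blood pressure, MENQOL-I, and BMD at 1 year and 2 years". Section 8.2.1 and Table 3 collect baseline values, including "BMD (DEXA bone density measurement of lumbar spine and hip". Section 8.4 does the same for the sub-study markers.

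**The concern.** The general rule and the repeated-measures rule apply to the same outcomes and do not give the same covariates. The second is the more specific. It names linear models for continuous outcomes and states its own adjustment list, which stops at the minimisation variables. If it governs, the baseline clause in the sentence before it has no continuous secondary outcome left to apply to.

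Two things are at stake. The first is precision: the baseline value is usually the strongest single predictor of a continuous outcome, and here it is already collected. The second is pre-specification: an analyst could fit either model and claim to follow the protocol. That matters more in a trial where participants and site staff know the allocation.

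**Working it through.** **Step 1. Which outcomes fall under the repeated-measures sentence?** From section 2.2.2, section 8.4 and Table 3:

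| Continuous secondary outcome | Follow-up times | Baseline collected |
|---|---|---|
| Lumbar spine and hip BMD | 1 and 2 years | yes |
| MENQOL-I, SAQ, WPAI | 3, 6, 12 months, then annually | yes |
| Weight, systolic and diastolic BP | 3, 6, 12 months, then annually | yes |
| Bone markers (sub-study) | 3 and 12 months | yes |
| Cardiovascular markers (sub-study) | 3 and 12 months, then annually | yes |

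None has a single follow-up time, so the two rules meet on every row. Lumbar spine BMD is the one row whose model is already fixed elsewhere, by the primary analysis.

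**Step 2. The protocol's own sample size.** Section 13.1.1 gives a difference of 0.05 g/cm², SD 0.15, 90% power, two-sided 5% and a correlation of 0.6 between follow-up measures.

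- Unadjusted n per arm = 2 × [0.15 × (1.960 + 1.282) / 0.05]² = 189.13.
- Times (1 + 0.6)/2 = 0.8 gives 151.3, rounded up to 152 per arm, or 304 in total.
- 304 / 0.8 = 380.

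Both stated figures, 304 and 380, are reproduced. The 152 per arm is used below.

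**Step 3. Precision with and without baseline.** For a contrast at one follow-up time, adding the baseline value as a linear covariate multiplies the variance by (1 − r²). Hence SE(adjusted)/SE(unadjusted) = sqrt(1 − r²), and leaving baseline out widens the confidence interval by 1/sqrt(1 − r²). The protocol gives no r, so the values below are assumptions. The 0.4 to 0.6 that it calls typical refers to correlation between follow-up measures.

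The SE column uses the only SD in the protocol, 0.15 for lumbar spine BMD. It shows scale only, because that outcome is already baseline-adjusted as the primary outcome. The protocol gives no SD for the other outcomes.

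Unadjusted SE = 0.15 × sqrt(2/152) = 0.0172.

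| Assumed r | sqrt(1 − r²) | SE with baseline | CI wider without baseline |
|---|---|---|---|
| 0.4 | 0.917 | 0.0158 | 9% |
| 0.6 | 0.800 | 0.0138 | 25% |
| 0.8 | 0.600 | 0.0103 | 67% |

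**Step 4. Check in a two-visit mixed model.** A simulation used 380 randomised, 20% missing at year 2 and one common correlation among baseline, year 1 and year 2. It gave these SEs for the year-2 contrast:

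| Correlation | SE without baseline | SE with baseline | Ratio |
|---|---|---|---|
| 0.4 | 0.0168 | 0.0157 | 1.07 |
| 0.6 | 0.0162 | 0.0132 | 1.23 |
| 0.8 | 0.0160 | 0.0100 | 1.60 |

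The year-1 data recover a little of the loss, so the ratios are slightly below those in step 3. Mean estimates were close to the true 0.05 under both models, so neither is biased.

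**The case against.** **The baseline clause may carry over.** The repeated-measures sentence does not say *only*. It covers linear and logistic models together, so it may name just the covariates common to both, with baseline for continuous variables understood from the sentence before. A reading that empties the preceding clause is also suspect as a reading of intent. This is plausible, and the omission may be a drafting slip. It does not remove the conflict: the sentence states its own list, whereas the primary-analysis and route-comparison text names or imports baseline outright.

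**Baseline could enter as part of the response.** Section 13.1.1 describes repeated-measures data that include a baseline. Such a model would recover much the same precision. But section 13.3 does not say this for secondary outcomes, and its primary model uses baseline as a covariate. Details may be left to the SAP, but here the protocol itself fixes the covariates, in two ways.

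**Other mitigation.** Section 13.3 permits, but does not require, the primary outcome's sensitivity analyses for key secondary outcomes. These include adjustment for markedly imbalanced baseline variables. For weight, the BMI minimisation factor recovers part of the loss.

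**Two stronger readings that the protocol does not support.**

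- *Two models for 2-year lumbar spine BMD, hence two estimates.* A reader might infer this because the measurement is both the primary outcome and a listed secondary one. But the primary model already yields the 1- and 2-year contrasts, and nothing orders a second fit. The double listing is an editorial matter.
- *Main comparisons less precise than the route comparisons.* A reader might infer this because only the latter are clearly baseline-adjusted. But the route comparisons split the HRT arm. With a 50% route share (76 against 152) and r = 0.5, the adjusted route SE is 0.15 × sqrt(1/152 + 1/76) × 0.866 = 0.0182, against 0.0172 for the unadjusted main comparison. The order reverses only when 1 − r² falls below (2/152)/(1/152 + 1/76) = 2/3, that is r above about 0.58. At a 20% share (30.4 against 152) the bound is 1/3, that is r above about 0.82.

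**Conclusion.** The concern holds as an inconsistency in the covariate rule for continuous secondary outcomes. Followed literally, the repeated-measures sentence leaves the baseline value out of the randomised comparison of hip BMD, MENQOL-I, SAQ, WPAI, weight, blood pressure and the sub-study markers. The cost is precision and an unambiguous plan. Validity is not at stake, and the primary analysis is untouched.

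The direction of the loss is certain for any non-zero r. Its size is not, because r is assumed and will differ between outcomes. This should be corrected but does not threaten the trial's main conclusion.

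**What to change.** Reword the repeated-measures sentence in section 13.3 along these lines: *mixed-effect models with the minimisation variables and, for continuous outcomes, the baseline value of that outcome where collected, as covariates, each with a time interaction as in the primary analysis.* Add one sentence stating that the lumbar spine BMD contrasts at 1 and 2 years are taken from the primary model. Carry the same wording into the SAP.

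The cost is two sentences. The baselines are already collected. Section 13.3 has the SAP agreed before the 2-year database lock, and section 6.3 keeps the trial statisticians blinded until that lock, so the change can be made without knowledge of results by arm.

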The two preparations widely prescribed in the UK as oestrogen replacement for women with POI are the combined oral contraceptive pill (COC) and hormone replacement therapy (HRT). These preparations have different oestrogen formulations and may have differing benefits and risks. At present there are no robust data to inform women’s decision-making. This results in variations in clinical practice and varying advice that may be confusing. For some women, the choice between the COC or HRT may depend upon contraceptive needs or acceptability of the treatment, but if both are acceptable alternatives, women need to have the information to help make an informed decision.

The COC may be seen as socially acceptable for young women and may reduce the stigma associated with menopause. It is also free of prescription charges in England. The COC, unlike HRT, provides contraceptive cover. Contraception may be desired as 5–10% of women with POI still conceive spontaneously¹². However, HRT provides physiological replacement of oestrogen and might therefore be a better option for sustaining long-term health. There is some limited evidence to suggest that HRT is superior to the COC in increasing/maintaining bone density, however the strength of this evidence is insufficient to change current clinical practice. Even small differences between treatments may have a large impact on long-term health outcomes, because women with POI are taking hormone

Trial name:	Premature Ovarian Insufficiency Study of Effectiveness of hormonal therapy	Protocol version:	4.0	date:	01 Oct 2024	Page:	16
-------------	--	-------------------	-----	-------	-------------	-------	----

replacement for many years, so it is important to establish definitively the superiority/non-superiority of HRT over the COC.

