2.1.2. Secondary objectives -effectiveness

- To assess the relative effectiveness, of HRT (any route) compared to the COC on menopausal symptoms, quality of life, sexual functioning, weight, and blood pressure.
- To assess the effect of treatment with HRT (any route) compared to COC on adherence with treatment, pregnancy outcome, side effects and serious adverse events.
- To assess the relative effectiveness of oral and transdermal HRT, compared to the COC in terms of BMD, blood pressure and menopausal symptoms.
- To compare the prevalence of bone fractures, diagnosis of cardiovascular disease, cancer, cognitive impairment and mortality between women treated with HRT (any route) and those treated with COC.

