9.2. Adverse Events and reporting requirements/procedures

The collection and reporting of Adverse Events (AEs) will be in accordance with the Medicines for Human Use Clinical Trials Regulations 2004 (and subsequent amendments).

All IMPs (HRT and COC) being used in this trial are licensed and have well characterised safety profiles.

All preparations of HRT used in this trial are licensed for use for oestrogen deficiency symptoms in post- and peri-menopausal women.

Whilst the COC is licensed as an oral contraceptive it is not licensed specifically for treating oestrogen deficiency and POI. It is however widely, prescribed for the treatment of POI; this off-label use is standard practice and all treatments used in the trial have well-established safety profiles.

In order to provide secondary outcome data about the adverse events associated with the use of the COC or HRT, only specified adverse events will be collected.

The following expected AEs will be participant-reported and collected using a questionnaire at 3, 6, 12 months and yearly up to 5 years, depending on the point at which the participant joins the trial. If a

Trial name:
	
Premature Ovarian Insufficiency Study of Effectiveness of hormonal therapy
	
Protocol version:
	
4.0
	
date:
	
01 Oct 2024
	
Page:
	
36

--------------------	---	--------------------------	------------	--------------	--------------------	--------------	-----------

clinic visit is not possible or a participant fails to attend, questionnaires will be provided to participants electronically so they can be completed remotely.

Participants will be asked at each follow-up visit if they have experienced any of the following:

- Unscheduled bleeding
- Breast pain
- Nausea
- Headaches
- Skin or hair changes (acne/facial spots, greasy or oily skin, hair loss/hair thinning, hirsutism (=excessive hair growth on face or body))
- Dysmenorrhoea (period pains)
- Menorrhagia (heavy periods)
- Premenstrual syndrome (PMS)
- VTE or pulmonary embolism (PE)
- Broken bone(s)

Where any of the above events result in an admission to hospital or prolongation of a hospital stay this will also require reporting on a SAE form by the Principal Investigator or delegate (see section 9.3).

Adverse events will be coded using the Medical Dictionary for Regulatory Activities (MedDRA) as per NCTU standard practice.

9.3.Serious Adverse Events and reporting requirements

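### Common solicited side effects are part of a comparative secondary objective, but section 13.3 plans no between-group estimate with an interval for them (low priority)

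*Protocol*

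**What the plan says.** The second secondary objective (protocol section 2.1.2) is comparative: "To assess the effect of treatment with HRT (any route) compared to COC on adherence with treatment, pregnancy outcome, side effects and serious adverse events".

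Section 2.2.2 lists adverse events among the secondary outcomes, at 3, 6 and 12 months and then annually, and names some of them: "Specific minor-side effects collected will include breast pain, nausea, headaches, skin or hair changes and unscheduled bleeding".

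Section 9.2 gives the purpose of collecting the specified events: "In order to provide secondary outcome data about the adverse events associated with the use of the COC or HRT". The items are put to everyone in the same way: "Participants will be asked at each follow-up visit if they have experienced any of the following".

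Section 13.3 sets a general rule, "Between-group comparison of secondary outcomes will be based on an appropriate regression for the outcome adjusted for the minimisation variables", and for repeated measures a mixed model (logistic for binary outcomes) giving the group difference at each time point. Adverse events then get a rule of their own: "Adverse events will be presented descriptively only and will be summarised according to both the allocated group and the treatment received". The same section also promises: "Descriptive statistics appropriate for the outcome will also be presented for all outcomes at all collected time points by treatment group". The descriptive statistics it names are means, standard deviations, medians, quartiles, extremes, frequencies and percentages. No interval is among them.

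**The concern.** The objective asks for an effect of one treatment relative to the other. The items are asked systematically in both arms and are called secondary outcome data, yet they are taken out of the rule that gives other secondary outcomes a between-group estimate. The trial report could therefore follow the plan exactly and never say how large a side-effect difference is, or how uncertain.

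Side effects bear on the choice the trial is meant to inform. The background (section 1.1) says that where both treatments are acceptable, "women need to have the information to help make an informed decision". Percentages without intervals invite readers to make too much of small gaps, or to dismiss real ones.

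The concern is limited to eight common items: unscheduled bleeding, breast pain, nausea, headaches, skin or hair changes, dysmenorrhoea, menorrhagia and premenstrual syndrome. Descriptive reporting is reasonable for serious events, VTE or pulmonary embolism, and broken bones, which can be expected to be rare.

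**Working it through.** **Step 1: is an estimate planned anywhere?** Set side by side, objective 2 is comparative, section 2.2.2 makes adverse events a secondary outcome, and section 9.2 says the solicited items supply that outcome. In section 13.3 the specific rule for adverse events overrides the general one through the word *only*. No other part of the protocol plans a between-group estimate for side effects. If the general rule were read as still applying to them, two sentences of section 13.3 would conflict and one would need rewording anyway.

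**Step 2: arm sizes.** Section 13.1.1 gives 304 analysed and 380 recruited. Check: per arm, 2 × [0.15 × (1.960 + 1.282)/0.05]² ≈ 189.1. Multiplying by (1 + 0.6)/2 = 0.8 gives 151.3, so 152 per arm and 304 in total, and 304/0.8 = 380. The stated figures reproduce. They are used here only to size the arms: 152 per arm if 20% do not return a questionnaire (borrowing the protocol's loss figure), 190 if all do.

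**Step 3: assumptions.** The protocol gives no side-effect rates, no item-level return rates and no hysterectomy share. Assumed: 10–50% report an item on a given questionnaire, and 0–20% have had a hysterectomy. Bleeding and period items could then have as few as 152 × 0.8 = 121.6, rounded up to 122, per arm.

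**Step 4: precision at one questionnaire.** Half-width of the 95% interval = 1.96 × √(2p(1−p)/n), in percentage points:

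| n per arm | p = 10% | 20% | 40% | 50% |
|---|---|---|---|---|
| 122 | 7.5 | 10.0 | 12.3 | 12.5 |
| 152 | 6.7 | 9.0 | 11.0 | 11.2 |
| 190 | 6.0 | 8.0 | 9.9 | 10.1 |

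**Step 5: what an interval would tell a reader.** Lower 95% limit (Wald) when the arms differ by 7 or 10 points, with p the lower-arm proportion:

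| n per arm | gap | p = 10% | 20% | 40% | 50% |
|---|---|---|---|---|---|
| 122 | 7 | −1.5 | −3.6 | −5.4 | −5.5 |
| 152 | 7 | −0.6 | −2.5 | −4.1 | −4.2 |
| 190 | 7 | 0.2 | −1.5 | −2.9 | −3.0 |
| 122 | 10 | 1.1 | −0.8 | −2.4 | −2.4 |
| 152 | 10 | 2.1 | 0.3 | −1.1 | −1.1 |
| 190 | 10 | 2.9 | 1.4 | 0.05 | 0.05 |

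A 7-point gap has an interval that includes zero in 11 of 12 cells. A 10-point gap excludes zero in 7 of 12, two of them only just.

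**Step 6: number of intervals the fix creates.** 8 items × 4 questionnaires = 32, and 32 × 0.05 = 1.6 expected to exclude zero by chance if nothing differed. With the four skin and hair effects reported separately, 11 × 4 = 44 and 44 × 0.05 = 2.2.

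**The case against.** Descriptive reporting of adverse events is common and looks deliberate here. A specific rule that overrides a general one is a choice, and assessing an effect does not by itself require a model or an interval. Serious events sit in the same objective, and descriptive reporting is accepted for them. Counts by randomised group will be tabulated, so a reader can work out a crude interval. The phrase could also be read as ruling out only formal tests, in which case the SAP could add intervals to the tables. All of this stands. It makes the point an improvement and not the correction of a mistake.

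Two further objections limit how the estimates can be used, and both stand. Table 3 shows no baseline entry for adverse effects of treatment, whereas MENQOL-I, SAQ and WPAI are collected at baseline. Pre-existing headaches or skin complaints therefore cannot be separated out, although randomisation still allows the arms to be compared. Bleeding also depends on regimen: flexible extended COC use takes its breaks in response to breakthrough bleeding, and HRT progestogen may be cyclical, continuous or intrauterine (sections 7.1.1 and 7.1.2). A pooled difference for these items needs that caveat.

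Open-label self-report does not explain the exemption. The three questionnaires named above are also unblinded self-report, and they do get between-group estimates.

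A reader might infer that the trial will leave side effects uncompared, or that the protocol is plainly in error. The documents do not support either reading: side-by-side rates by allocated group are promised, and satisfaction and change or cessation of treatment fall under the general rule for between-group comparison.

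**Conclusion.** The point holds as a cheap, low-priority improvement. One part of one secondary objective is comparative, and its analysis stops at percentages by arm. No figure in the protocol is wrong, and the primary analysis is untouched.

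Over the assumed ranges, the missing intervals would have half-widths of 6.0–11.2 points for items asked of all women and up to 12.5 for bleeding and period items. They would help most in judging gaps of about 10 points or less. These sizes rest on assumed event rates, return rates and hysterectomy share. They show how precise the estimates might be, not that any conclusion of the trial would change.

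**What to change.** Amend section 13.3 as follows.

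- For the eight common solicited items (skin or hair changes as one item), report by allocated group the risk difference or odds ratio with a 95% CI and no p-value.
- Do this at each questionnaire up to 2 years: 3, 6 and 12 months and 2 years. The early questionnaires matter because section 7.3 expects adherence to fall. Women who stop or switch because of an early side effect may no longer report it later.
- Restrict unscheduled bleeding, dysmenorrhoea and menorrhagia to women with a uterus, and state that they depend on the regimen used. Hysterectomy status is already needed for the subgroup analysis in section 13.3.4.
- Base each estimate on women who returned that questionnaire, and show return rates by arm.
- Label the intervals as estimation only: no multiplicity control, open-label reporting, no baseline measure of these items.
- Keep serious events, VTE or pulmonary embolism, broken bones and other rare events descriptive.
- Label the summary by treatment received as supportive and non-randomised.

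The cost is a short addition to the text and simple calculations on data already being collected. The main downside is the 32 uncontrolled intervals. They do not remove reporting bias, and they describe only the women who responded.
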